ENDPOINTS:

Primary Endpoint

- One point decrease from baseline in target lesion Global PG (GPG) Severity Score at Week 16

Secondary Endpoints

- Complete re-epithelization of PG lesions (GPG Severity Score of 0) at visits 3, 4, 5, 6, 7, 8, and 9.
- Absolute change from baseline in patient-reported pain severity (Pain-VAS) at visits 3, 4, 5, 6, 7, 8, and 9 and at complete re-epithelization of ulcer.
- Absolute change in quality of life (DLQI) from baseline at visits 3, 4, 5, 6, 7, 8, and 9 and at complete re-epithelization of ulcer.
- Recurrence of PG lesions after complete re-epithelization (GPG score 0) of all lesions and spesolimab cessation

- Time to worsening (1 or more GPG point increase) of target PG lesion from spesolimab cessation

STUDY DESIGN OVERVIEW:

This study is a prospective, proof-of-concept, open label clinical trial. The study will take place at Icahn School of Medicine at Mount Sinai.

The study will screen up to 25 subjects in order to enroll a total of up to 20 patients with at least one clinically measurable ulcerative PG lesion. Subjects will receive 900 mg of spesolimab intravenously (IV) over 90 minutes at a frequency of every 4 weeks until Week 28 with the following exceptions:

- At the Week 8 visit, subjects who do not show any improvement, show only minimal improvement, or those that begin to lose their initial improvement response (decrease in pain or wound drainage), may be switched to a dosing frequency of every 3 weeks through Week 26, at the discretion of the investigator. These subjects will still return at Week 16 for an endpoint visit, but will not receive treatment at this visit. Refer to Tables 3 and 4 for schedule of events.

All subjects will be monitored monthly for 4 months subsequent to treatment cessation.

Subjects who reach GPG score 0 at anytime during the study will continue to receive treatments until week 28 (or Week 26 depending on dosing frequency) and will then be monitored for 4 months subsequent to treatment cessation.

Subjects who are experiencing improvement in their PG but who have not reached complete wound healing will continue treatment until Week 28 (or Week 26 for those who were switched to every 3 week dosing), even if primary endpoint has been achieved. These subjects will then be monitored for 4 months subsequent to treatment cessation.

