Contraindications to spesolimab treatment include patients with severe or life-threatening hypersensitivity to spesolimab or to any of the excipients in spesolimab¹⁴. In our experience, patients infused with spesolimab exhibited no adverse reactions during or after treatment with no pre-medication required. There is limited data available on the impact of antidrug antibodies on safety and efficacy upon retreatment. Furthermore, it is not known whether spesolimab increases or decreases the efficacy of other medications.

PRIOR TREATMENT:

All relevant treatment received by the subject within 30 days before screening will be recorded.

CONCOMITANT TREATMENT:

Concomitant medications are permitted for the treatment of stable, chronic illness as well as for pyoderma gangrenosum. Concomitant treatments for pyoderma gangrenosum will tapered over spesolimab treatment course as tolerated. Use of such concomitant medication or other medications that may be required throughout the study will be recorded (including the reason for treatment and name, dose, unit, route, and the date of treatment as appropriate) until treatment termination and throughout follow-up period. Patients will be allowed to continue with biologic therapies used to treat comorbidities.

PROHIBITED TREATMENT:

All treatments prohibited by clinician during the screening period are also prohibited throughout the course of the study. No live attenuated vaccinations are permitted throughout the study.

PROCEDURES:

Monitoring of AEs will begin at the time of signing the informed consent form and will be continued throughout the course of the study. All study procedures will be completed at designated times during the study period (see Tables 3 and 4). Subjects will receive 900mg IV spesolimab at a frequency of every 4 weeks through Week 8, at which time, at the discretion of the investigator, dosing frequency may be increased to every 3 weeks. Subjects will continue to dose every 4 or 3 weeks through Week 28 or 26 (depending on

dosing frequency). Subjects will be monitored once a month, for 4 months after treatment cessation. Patients that, in the opinion of the investigator, are benefiting from treatment at week 28 but need more therapy to achieve wound closure may be eligible to continue on treatment (on case-by-case basis) to a maximum of 52 week after discussion with Boehringer Ingelheim trial team.

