- Urine pregnancy test for all female subjects of child-bearing potential to confirm subject is not pregnant
- Collect blood samples for CBC with differential, CMP, and C-reactive protein (CRP), serum cytokine profiling (O-link® inflammatory cytokine panel, IL-1 β , and IL-36 subtypes), Nab, ADA, and Pre- and post dose pharmacokinetics.
- Administer study drug

Spesolimab Treatment Phase

Visits 3 thru 9 (subjects that dose every 4 weeks) or Visits 3 thru 11 (subjects that are switched to every 3 week dosing at Week 8)

- Record concomitant medications (including use of pain medication) and adverse events
- Urine pregnancy test for all female subjects of child-bearing potential to confirm subject is not pregnant
- Patient Pyoderma Gangrenosum Questionnaires and DLQI
- Obtain vital signs
- Standardized clinical photography of target lesion and other PG lesions
- PG clinical assessments (including number/location/measurements of PG lesions and GPG score for target lesion)
- Assess status of associated comorbid conditions (improved, no change, worse)
- Collect blood samples for CBC with differential, CMP, and C-reactive protein (CRP)
- **Only at Week 8 and Week 28 (subjects dosed every 4 weeks) or Week 26 (subjects switched to dosing every 3 weeks):** Nab, ADA, and pre dose pharmacokinetics.
- **Only at Week 16:** serum cytokine profiling (O-link® inflammatory cytokine panel, IL-1 β , and IL-36 subtypes), Nab, ADA, and pre dose pharmacokinetics.
- Administer study drug

Post-Spesolimab Follow-up Phase

Visits 10 thru 13 (subjects dosed every 4 weeks) or Visits 12-15 (subjects switched to dosing every 3 weeks)

Follow-Up Visits at 1 Month, 2 Months, 3 Months and 4 Months Post-Spesolimab Treatment Cessation

- Record concomitant medications (including use of pain medication) and adverse events
- Patient Pyoderma Gangrenosum Questionnaires and DLQI
- Assess status of associated comorbid conditions (improved, same, worse)
- Standardized clinical photography of target lesion and other PG lesions

- PG clinical assessments (including number/location/measurements of PG lesions, and GPG score of target lesion)
- Collect blood for serum cytokine profiling (O-link® inflammatory cytokine panel, IL-1 β , and IL-36 subtypes)
- If subject worsens or sees progression of their PG during the 4- month follow-up period (defined as 1 or more increase in GPG score of target lesion), then patient will be discontinued from the study and started on available, standard PG therapies.

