Demographics and Other Baseline Characteristics

Descriptive statistics of demographics and other baseline characteristics of patients will be summarized with mean, median, and standard deviation for quantitative outcomes, and frequency and percentage tables for categorical outcomes.. Other baseline characteristics include sex, age, height, weight, vital signs, duration of PG, history of pathergy or PG trigger (if known), concurrent diagnoses from medical history and indications for concomitant medication, concomitant medication, and previous PG treatments.

Target Lesion Measurement and Digital Image Assessments

Size of target PG lesion will be approximated at each visit by measuring the length, width and depth of the lesion. Target lesion will also be analyzed using Image J software to obtain a more precise surface area of each lesion using digital photographs taken at each visit.

Analysis of Primary Endpoint

We will compare the proportion of patients achieving one-point decrease in target lesion GPG score at Week 16 with a constant p=0.10. Clopper-Pearson 90% confidence interval will be estimated.

Analysis of Secondary Endpoints

- One sided Clopper-Pearson 90% confidence intervals will be estimated for the proportion of patients achieving re-epithelization (GPG Severity Score of 0) at Visits 3, 4, 5, 6, 7, 8, and 9
- We will apply a two-sided paired t-test to evaluate significance of the mean difference of GPG score at Week 16 versus Week 0.
- Mean patient reported scores of pain (Pain VAS) and quality of life (DLQI) at baseline will be compared to those at Week 16 and treatment termination using the student's t- test to compare between subject's pre and post-treatment scores.
- One sided Clopper-Pearson 90% confidence intervals will be estimated for the proportion of patients with recurrence or worsening of PG lesions from point of complete re-epithelization or spesolimab cessation at end of treatment visit (Week 28 or Week 26 depending on dosing frequency).

Interim Analysis

An interim analysis will be performed after the first 10 subjects complete Week 16. We will continue enrollment during this time. Proportion of patients achieving one-point GPG score decrease will be reported. Changes from baseline at Week 16 in the PG lesions (number, size, GPG score) will be evaluated and reported. Enrolled subjects will continue to receive treatments during this time.

Data Transfer and Management

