Data including the patient info, demographics, clinical scores will be stored in password-protected files that will be shared only with investigators and a biostatistical team, if necessary. Data will be stored on secure Mount Sinai servers that may only be accessed by investigators listed on this protocol.

Analysis of Safety and Tolerability

Safety will be evaluated by tabulations of adverse events (AEs) and will be presented with descriptive statistics at each visit. AEs will be coded using the CTCAE, Common Terminology Criteria for Adverse Events, V 4.0 and MedDRA. The number and percentage of subjects/lesions experiencing an AE/SAE will be stratified by system organ class, or a preferred term, and/or severity of the adverse event, and recorded and tabulated overall by each sub-strata. Each subject will be counted only once within a system organ class or a preferred term using the adverse events with the highest severity within each category. All information pertaining to adverse events noted during the study will be listed by subject, detailing verbatim given by the investigator, preferred term, system organ class, date of onset, date of resolution, severity, and relationship to treatment. A tabulation of AEs will be provided by subject.

Table 3. Schedule of Events Q4 Week Dosing Through Week 28

Visit Week	(Up to -28 Days before Baseline)	0	4	8	12	16	20	24	28	4 wk post-spesolimab last dose	8 wk post-spesolimab last dose	12 wk post-spesolimab last dose	16 wk post-spesolimab last dose		
Visit #	1	2	3	4	5	6	7	8	9	10	11	12	13		
Visit Type	Screening	Baseline	TX	TX	TX	TX	TX	TX	TX	F/Up	F/Up	F/Up	F/Up	Early Term (ET)	Additional Treatment Visits
Informed Consent	X														
Inclusion/Exclusion Criteria	X	X													
Demographics/Medical Hx ¹	X														
Limited Physical Exam	X	X													
Vitals ²	X	X	X	X	X	X	X	X	X					X	X
Serum Preg Test	X														
Urine Preg Test		X	X	X	X	X	X	X	X					X	X
CBC w/differential, CMP and CRP	X	X	X	X	X	X	X	X	X					X	X
Screening for TB (Quantiferon Gold, or PPD), HIV, HepB and HepC	X														
PG Clinical Assessments (including number location and measurements)	X	X	X	X	X	X	X	X	X	X	X	X	X	X	X
Global PG (GPG) Severity Score	X	X	X	X	X	X	X	X	X	X	X	X	X	X	X
Subject PG Questionnaire DLQI		X	X	X	X	X	X	X	X	X	X	X	X	X	X

Visit Week	(Up to -28 Days before Baseline)	0	4	8	12	16	20	24	28	4 wk post-spesolimab last dose	8 wk post-spesolimab last dose	12 wk post-spesolimab last dose	16 wk post-spesolimab last dose		

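### Healing is reported only as separate proportions at Visits 3 to 9, which give neither the number ever healed nor the time to healing, and stop at Week 20 for subjects switched to every-3-week dosing

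*Combined protocol and SAP*

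**What the plan says.** Under Endpoints, the healing endpoint is "Complete re-epithelization of PG lesions (GPG Severity Score of 0) at visits 3, 4, 5, 6, 7, 8, and 9". Analysis of Secondary Endpoints uses the same list: a one-sided 90% Clopper-Pearson interval for the "proportion of patients achieving re-epithelization (GPG Severity Score of 0) at Visits 3, 4, 5, 6, 7, 8, and 9". No proportion ever healed and no time to healing is defined. The one time-to-event endpoint concerns the period after treatment: "Time to worsening (1 or more GPG point increase) of target PG lesion from spesolimab cessation".

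Healed subjects stay on treatment and keep being scored. The Study Design Overview states "Subjects who reach GPG score 0 at anytime during the study will continue to receive treatments until week 28", or Week 26 on the switched schedule. Under Procedures, the treatment phase is Visits 3 to 9 on the every-4-week schedule, or "Visits 3 thru 11 (subjects that are switched to every 3 week dosing at Week 8".

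Procedures also allow a longer course for subjects who "need more therapy to achieve wound closure may be eligible to continue on treatment (on case-by-case basis) to a maximum of 52 week". Tables 3 and 4 have a column headed "Additional Treatment Visits", and the GPG row is marked in it, as it is at all four follow-up visits and at early termination.

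Two other secondary endpoints touch on healing: recurrence after all lesions have re-epithelialized and the drug has been stopped, and change in pain and DLQI at the time of re-epithelization.

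**The concern.** Whether and when ulcers close is a central clinical question in this trial, and the extension is offered in order to reach closure. A proportion at a visit describes who is healed that day. A subject who heals and reopens disappears from later proportions, and one who heals and then leaves may do so too. The plan expects such events: recurrence is an endpoint, some subjects are expected to lose their initial response, and subjects who worsen significantly are discontinued.

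The visit list also fits only one of the two schedules. Switching is offered to subjects with no, minimal or fading improvement at Week 8, so observation of healing ends earliest in the group that may heal late. If the analysis is run as written, the report cannot say how many of the 20 subjects healed or how long it took, and its last healing figure pools two different times.

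**Working it through.** The plan states no figure for healing. Its power statement concerns the primary endpoint and does not bear on this point.

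**1. Visit number against week.** From Tables 3 and 4:

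| Visit | Every 4 weeks (Table 3) | Switched (Table 4) | Difference |
|---|---|---|---|
| 3 | Week 4 | Week 4 | 0 |
| 4 | Week 8 | Week 8 | 0 |
| 5 | Week 12 | Week 11 | 1 |
| 6 | Week 16 | Week 14 | 2 |
| 7 | Week 20 | Week 16 | 4 |
| 8 | Week 24 | Week 17 | 7 |
| 9 | Week 28 | Week 20 | 8 |
| 10 | follow-up | Week 23, treatment | – |
| 11 | follow-up | Week 26, treatment | – |

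A pooled proportion is at a common week only for Visits 3 and 4. For switched subjects the endpoint omits Visits 10 and 11, the last 26 − 20 = 6 weeks of scheduled treatment. Extending the list to Visit 11 would not repair this, because Visits 10 and 11 are follow-up visits in Table 3.

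**2. What seven proportions say about ever healed.** Let x₃ to x₉ be the numbers healed at each visit among n = 20. Then

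- smallest possible number ever healed = the largest visit count;
- largest possible number = the smaller of n and the sum of the visit counts.

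The documents give no healing rates, so these counts are assumptions:

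| Healed at Visits 3–9 | Minimum | Maximum |
|---|---|---|
| 0, 0, 1, 2, 3, 3, 4 | 4 (20%) | 0+0+1+2+3+3+4 = 13 (65%) |
| 0, 1, 2, 3, 4, 5, 6 | 6 (30%) | min(20, 21) = 20 (100%) |

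In the first row, two-sided 90% Clopper-Pearson intervals would be 7.1% to 40.1% for 4/20 and 44.2% to 82.3% for 13/20. They do not overlap, so the ambiguity can exceed the sampling error. The maxima are extremes: 13 ever healed with 4 healed at Visit 9 needs 13 − 4 = 9 subjects who healed and were no longer counted as healed at Visit 9.

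**3. When the two agree.** If nobody reverses and nobody leaves, the last proportion equals the number ever healed by that visit. Even then, Visit 9 means Week 28 for some subjects and Week 20 for others.

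**4. What GPG 0 means.** Appendix 1 assigns score 0 to a point sum of 0 to 5. Erythema 1, elevation 1, purulence 0, active ulcer 1 (1–25%), granulation 1 and size 1 (up to 2 cm) total 5, which is GPG 0 with an open ulcer. The description beside that score says no ulceration is apparent, so sum and description can disagree. This matters for any first-healing outcome, which keeps an event once it is recorded.

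**The case against.** The strongest reply is that nothing is lost. GPG is scored at every treatment, follow-up, extension and early termination visit, so a cumulative proportion could be computed later. Healing is a secondary endpoint in a 20-subject open-label study, and limiting it to the common treatment period is defensible because extended subjects have longer to heal. Most of this stands: the gap is in the analysis plan, and the extension merits a descriptive count only. But the visit list does not deliver a common treatment period, and choosing the healing definition after seeing open-label results invites selective reporting.

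A reader might infer more than the documents support:

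- *That closure in the extension is used nowhere.* The recurrence endpoint and pain and DLQI at re-epithelization are not capped at Visit 9 and may use some of those dates. Coverage is incomplete: the planned recurrence analysis ties cessation to Week 28 or 26, and the planned pain and DLQI tests are at Week 16 and treatment termination. What is missing is a healing rate.
- *That the uncertainty is as wide as 5 to 20.* That follows if 5 of 20 are healed at every visit, but those counts are invented, and the upper end needs at least 15 subjects to heal and then cease to be counted as healed, although healed subjects stay on treatment.
- *That 24 of 52 treatment weeks (46%) go unused.* This assumes a full extension. Procedures allow it case by case, and Investigational Drug Supply speaks of select cases.

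A first-event outcome also has a weakness that visit-wise status lacks: it cannot revert, and GPG 0 does not guarantee a closed ulcer. That shapes the fix.

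**Conclusion.** The point holds as a gap in endpoint definition and analysis, and the plan should be changed. The firm part needs no assumed rates: for switched subjects the healing endpoint drops Weeks 23 and 26, and pooled proportions from Visit 5 onward mix weeks, by up to 8 weeks at Visit 9. That visit-wise proportions do not determine the number ever healed or the time to healing is also certain, unless healing never reverses and nobody leaves. The size of that second part is unknown; 4 to 13 of 20 illustrates it under assumed counts and is not a forecast. Closure first reached in the extension or in follow-up is in no healing-rate analysis. The primary endpoint and data collection are unaffected. Figure 3 and the text just before Endpoints could not be read, so this rests on Endpoints, Procedures, Statistical Considerations, Tables 3 and 4 and Appendix 1.

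**What to change.** In Secondary Endpoints and Analysis of Secondary Endpoints:

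1. Index healing by week or actual date instead of visit number, and include all on-treatment visits on both schedules.
2. Add, per subject, the cumulative proportion with a first GPG 0 of the target lesion, and the time to it from first dose. Report it at Week 16, which is a visit on both schedules, and at the end of scheduled treatment (Week 28, or Week 26 if switched), with a confidence interval. Subjects who leave unhealed stay in the denominator as not healed.
3. Report the same outcome also requiring 0% active ulcer, an item Appendix 1 already records.
4. Give closures first seen in the extension and in follow-up as a separate descriptive count, with the number of subjects extended.
5. Keep visit-wise status to show reversals and to serve the endpoint's wording, which covers PG lesions while GPG is scored on the target lesion.

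The cost is a few sentences and one curve or table, with no new assessments. The downside is that healing dates are known only to the visit interval: 1 to 4 weeks during scheduled treatment, and not stated for extension visits. The end-of-treatment estimate also combines Week 26 and Week 28, a 2-week difference to be stated beside it.

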PG Questionnaire		X	X	X	X	X	X	X	X	X	X	X	X	X	X	X	X

Visit Week	(Up to -28 Days before Baseline)	0	4	8	11	14	16	17	20	23	26	4 wk post-spesolimab last dose	8 wk post-spesolimab last dose	12 wk post-spesolimab last dose	16 wk post-spesolimab last dose		
Visit #	1	2	3	4	5	6	7	8	9	10	11	12	13	14	15		
Visit Type	Screening	Baseline	TX	TX	TX	TX		TX	TX	TX	TX	F/Up	F/Up	F/Up	F/Up	Early Term (ET)	Additional Treatment Visits
Standardized Photographs		X	X	X	X	X	X	X	X	X	X	X	X	X	X	X	X
Record and changes related to associated conditions (such as IBD, RA, etc) if applicable		X	X	X	X	X	X	X	X	X	X	X	X	X	X	X	
Serum Cytokine Profile O-Link Inflammatory Panel		X					X					X	X	X	X	X	
Pharmacokinetics, ADA, NAb ³		X		X			X				X					X	
Dispense Drug		X	X	X	X	X	X	X	X	X	X						
Concomitant Medications	X ⁴	X	X	X	X	X	X	X	X	X	X	X	X	X	X	X	X
Adverse Events	X	X	X	X	X	X	X	X	X	X	X	X	X	X	X	X	X

¹ Includes current and past medical conditions in addition to personal and family history of inflammatory bowel disease, rheumatoid arthritis, and autoimmune conditions as well as history of myeloproliferative disorders and malignancy

[figure not shown]
² Includes height and weight (only at screening), blood pressure, and pulse

³ Pre-dose PK, ADA, NAb samples will be obtained at selected visits (Visit 2, 4, 7 and 11, or ET). At Week 0/Visit 2, a post-dose PK samples will also be obtained approximately 5 mins after end of i.v. infusion.

⁴ Record all concomitant medications at each visit, and at screening also collect any medications taken within the last 30 days, and previous therapies/treatments for PG (including systemic and topical treatments, and invasive treatment such as surgery, radiation and cryotherapy).

Figure 3. Flow Diagram for Participants

REFERENCES

- ¹ Alavi, A., French, L. E., Davis, M. D., Brassard, A., & Kirsner, R. S. (2017). Pyoderma gangrenosum: an update on pathophysiology, diagnosis and treatment. *American journal of clinical dermatology*, 18(3), 355-372.
- ² Xu, A., Balgobind, A., Strunk, A., Garg, A., & Alloo, A. (2020). Prevalence estimates for pyoderma gangrenosum in the United States: an age-and sex-adjusted population analysis. *Journal of the American Academy of Dermatology*, 83(2), 425-429.
- ³ Cozzani, E., Gasparini, G., & Parodi, A. (2014). Pyoderma gangrenosum: a systematic review. *G Ital Dermatol Venereol*, 149(5), 587-600.

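### For subjects switched to every-3-week dosing, Table 4 and the treatment-visit list call for a Week 16 infusion that the design text rules out

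*Combined protocol and SAP*

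**What the plan says.** The Study Design Overview lets the investigator move a subject from every-4-week to every-3-week dosing at Week 8, continuing through Week 26. For these subjects it says: "These subjects will still return at Week 16 for an endpoint visit, but will not receive treatment at this visit". The next sentence reads: "Refer to Tables 3 and 4 for schedule of events". The Procedures section gives the tables similar authority: "All study procedures will be completed at designated times during the study period (see Tables 3 and 4".

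Investigational Drug Supply gives a total of 8 or 9 infusions, depending on the dosing frequency.

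Two places that staff would work from say something different:

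- In Table 4, the row "Dispense Drug" is marked at every visit from Visit 2 to Visit 11, including Visit 7 (Week 16).
- In Procedures, Spesolimab Treatment Phase, one list covers "Visits 3 thru 11 (subjects that are switched to every 3 week dosing at Week 8") as well as Visits 3 to 9 of the every-4-week schedule. Its last line is "Administer study drug", with no exception for Week 16.

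The same list describes the Week 16 blood draw as including "and IL-36 subtypes), Nab, ADA, and pre dose pharmacokinetics". Footnote 3 of Table 4 agrees: "Pre-dose PK, ADA, NAb samples will be obtained at selected visits (Visit 2, 4, 7 and 11, or ET"). Visit 7 in that footnote is Week 16.

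On a separate matter, the Physical Examination/Vital Signs paragraph requires a limited examination, blood pressure and heart rate at every visit. Both schedule tables place the examination at Screening and Baseline only and show no vital signs at the follow-up visits.

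**The concern.** The narrative withholds drug at Week 16 in switched subjects, while the schedule table and the visit list, which are what site staff use on the day, tell them to give it. The narrative itself sends the reader to that table. A coordinator or pharmacist working from Table 4 would prepare an infusion between the Week 14 and Week 17 doses, at intervals intended nowhere in the protocol. The protocol lists serious infection and systemic hypersensitivity among the potential risks still under evaluation, so an unplanned infusion should not be left to chance. Table 4 assessments from Week 17 onward would also follow an unplanned dose.

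The pre-dose label has the same origin. No dose is due at Week 16 in switched subjects, so the sample is not pre-dose in them, and anyone pooling Week 16 samples by label would combine different times since the last infusion.

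**Working it through.** **1. The stated infusion count reproduces under the design text.**

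- Every 4 weeks: Weeks 0, 4, 8, 12, 16, 20, 24, 28, so 28/4 + 1 = 8.
- Switched: Weeks 0, 4, 8, then every 3 weeks to Week 26 (11, 14, 17, 20, 23, 26), so 3 + (26 − 8)/3 = 3 + 6 = 9.

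Both agree with Investigational Drug Supply. The figure of 9 is reached only without a Week 16 dose.

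**2. Table 4 as printed.** The drug row aligned with the Visit Week and Visit Type rows:

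| Week | 0 | 4 | 8 | 11 | 14 | 16 | 17 | 20 | 23 | 26 |
|---|---|---|---|---|---|---|---|---|---|---|
| Visit | 2 | 3 | 4 | 5 | 6 | 7 | 8 | 9 | 10 | 11 |
| Visit type | Baseline | TX | TX | TX | TX | (blank) | TX | TX | TX | TX |
| Drug mark | X | X | X | X | X | X | X | X | X | X |

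There are 10 marks. The Visit Type cell is blank only at Week 16, which again points to no treatment at that visit. Table 3 has 8 drug marks and agrees with the text.

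**3. Could the mark be an artefact of reading the table?** No. A correct row has 9 marks, and losing a blank cell would still leave 9. Blank cells elsewhere in the table are preserved: the pharmacokinetic row is marked at Visits 2, 4, 7, 11 and early termination, as footnote 3 says. All the conflicting text is current, not from the amendment log.

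**4. Consequence of a literal reading, per switched subject.**

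| | Design text | Table 4 as printed |
|---|---|---|
| Infusions | 9 | 10 |
| Total dose | 9 × 900 = 8,100 mg | 10 × 900 = 9,000 mg |
| Intervals (weeks) | 4, 4, 3, 3, 3, 3, 3, 3 | 4, 4, 3, 3, 2, 1, 3, 3, 3 |
| Dose, Weeks 14 to 17 inclusive | 2 × 900 = 1,800 mg | 3 × 900 = 2,700 mg |

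The excess is 900 mg. The documents give no expected switch rate, so the number of subjects exposed to the error ranges from 0 to 20.

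**5. Week 16 pharmacokinetic sample under the intended plan.**

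- Table 3 subjects: previous dose at Week 12, so (16 − 12) × 7 = 28 days.
- Switched subjects: previous dose at Week 14, so (16 − 14) × 7 = 14 days.

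**6. Examination and vital signs.** The examination is marked at Visits 1 and 2 only. After Baseline it is therefore scheduled at 0 of 13 − 2 = 11 visits in Table 3 and 0 of 15 − 2 = 13 in Table 4. Vital signs are scheduled at 0 of 4 follow-up visits in each table.

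**The case against.** The strongest reply is that this is a clerical slip and no design decision is in dispute. The only sentence that addresses the question directly says no treatment. The 3-week interval, the infusion total, the title of Table 4 and the blank Visit Type cell all support it. At a single site, staff would have to infuse at Weeks 14, 16 and 17 under an every-3-week regimen without noticing. The treatment-phase list is generic and shared by two regimens with different visit numbering, so its drug line names no week and merely lacks an exception stated elsewhere. The Week 16 severity score is taken under either reading.

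Much of this stands. The error is one of consistency, and the extra dose is unlikely. It does not remove the need to correct a dosing schedule that contradicts the rule it is meant to carry out, particularly when the narrative and the Procedures section both defer to it. The shared list already restricts its sampling lines to particular weeks, so the missing dosing exception is a real omission.

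On the pharmacokinetic label, the objection is largely right. Relabelling changes no sampling time, and recorded dates would reveal time since infusion. Even true pre-dose samples would differ between regimens (21 versus 28 days). The visible text contains no pharmacokinetic endpoint or analysis. It remains a wording error worth correcting alongside the main one.

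The examination and vital-signs mismatch is a separate, minor issue. The visit lists and both tables agree with each other, one general sentence is the outlier, and extra safety evaluations are allowed when clinically indicated. It adds no weight to the dosing point.

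**Conclusion.** The concern holds and should be fixed. As written, the Table 4 drug mark at Visit 7 and the unqualified drug line in the treatment-phase list contradict the design text. The infusion count, dosing interval and Visit Type row show that the table and list are wrong. Taken literally, they add one 900 mg infusion per switched subject and shorten two intervals to 2 weeks and 1 week.

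This size assumes that staff follow the table over the narrative, which other text argues against, so it describes a preventable dosing error and not an expected outcome. The primary analysis does not depend on it. The pre-dose label is inaccurate for switched subjects but affects no analysis planned in the visible text. The examination and vital-signs discrepancy is real and minor: adverse events, concomitant medications, lesions and comorbidity status are still recorded at every follow-up visit, and vital signs and safety bloods at every treatment visit and at early termination.

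**What to change.** - **Table 4:** delete the drug mark at Visit 7 (Week 16).
- **Procedures, Spesolimab Treatment Phase:** qualify the drug line so that it excludes Visit 7 (Week 16) for subjects switched to every 3 weeks.
- **Pharmacokinetic label:** in Table 4 footnote 3 and in the Week 16 line of the same list, describe the sample in switched subjects as taken 2 weeks after the Week 14 infusion instead of pre-dose.
- **Physical Examination/Vital Signs (minor):** reconcile the paragraph with the schedule. Either limit it to the visits where these assessments are scheduled, or add them to the tables and visit lists.

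The first three changes are a minor amendment with no added procedures. With the Week 16 dose removed, Table 4 gives 9 infusions and agrees with the rest of the protocol. Limiting the examination paragraph also costs nothing. Adding the assessments instead would mean up to 11 (Table 3) or 13 (Table 4) further limited examinations per subject, and vital signs at 4 follow-up visits.
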